## **2.2. Pooling Algorithm for Analysis Centers**

Not planned, subgroups analyses by country are described in section [2.4](#).

## **2.3. Analysis Sets**

### **2.3.1. Full Analysis Set**

The Full Analysis Set (FA) will consist of all subjects who were randomized and who received at least one dose of study vaccine. This will be the primary population for all analyses (except immunogenicity, see below) described in this document.

### **2.3.2. Per-Protocol Immunogenicity Analysis Set**

The per protocol immunogenicity (PPI) population consist of all subjects who have received at least the first three vaccinations, according to the protocol-specified vaccination schedule (+/- 2 weeks), have at least one measured post-dose blood sample collected and were not diagnosed with HIV during the study. Samples taken after Week 48 from subjects in the PPI population who missed the 4th vaccination or did not receive the 4th vaccination in the protocol-specified time window (+/- 2 weeks) will be excluded from the analysis.

The analysis of the immune responses will be performed on the per protocol immunogenicity population.

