4.3. Prohibitions and Restrictions

Potential subjects must be willing and able to adhere to the following prohibitions and restrictions during the course of the study to be eligible for participation:

1. Agree to follow the contraceptive requirements as noted in Section 4.1 during the main study.
2. Following vaccination subjects may be excluded from donating blood products due to induced vaccine seropositivity (see Section 9.4.3) for as long as VISP persists.
3. Male subjects must agree not to donate sperm from the first administration of study vaccine/placebo until 3 months after the last dose of study vaccine/placebo.
4. Female subjects must agree not to donate eggs (ova, oocytes) for the purpose of assisted reproduction until 3 months after the last dose of study vaccine/placebo.
5. Use of any experimental medication (including experimental vaccines other than the study vaccine) during the main study is disallowed. Vaccination with any licensed vaccine within 14 days prior to or after any of the study vaccinations is disallowed. However, if a vaccine is indicated in a post-exposure setting (eg, rabies or tetanus), it must take priority over the study vaccine. Subjects who enter the optional LTE phase are allowed to use any experimental medication during the optional LTE phase, except for prophylactic or therapeutic HIV vaccine candidates which are disallowed and experimental immunomodulators/suppressors which need prior sponsor approval.
6. Chronic or recurrent use of immunomodulators/suppressors, eg, cancer chemotherapeutic agents, and oral or parenteral corticosteroids is prohibited during the main study. During the optional LTE phase, use of these medications is discouraged, except when required by

the medical condition of the subject, and each use should be reported during clinical visits. Inhaled, ocular, and topical steroids are allowed (see Section 8).

7. Concurrent participation in another clinical study without prior sponsor approval is disallowed during the main study. Subjects who enter the optional LTE phase are allowed to participate in another clinical study, except for studies with prophylactic or therapeutic HIV vaccine candidates which are disallowed and studies with experimental immunomodulators/suppressors which need prior sponsor approval.

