4.4. Inclusion and Exclusion Criteria for the Optional Long-term Extension Phase

Each potential subject must satisfy all of the following inclusion criteria to be enrolled in the optional LTE phase of the study upon completion of the final main study visit at Week 72. For the optional 2-year extension of the LTE phase, there are no inclusion criteria, except for the signing of the ICF appendix in criterion 1.

1. Each subject must sign an ICF appendix for the optional 3-year LTE phase indicating that he or she understands the purpose of and procedures required for the optional LTE phase and is voluntarily willing to participate in the optional LTE phase of the study. Subjects willing to participate in the optional 2-year extension of the LTE phase will need to sign the ICF appendix for the 2-year extension at Visit 23.
2. Subject must be randomized to Group 2A of the main study.

Note: Upon sponsor unblinding at the Week 28 analysis, subjects randomized to Group 2A who have received all 4 vaccinations, will be asked to participate in the optional LTE phase and sign the ICF appendix for the optional LTE phase at Week 72. Subjects who attend their Week 72 visit prior to the sponsor's unblinding at the Week 28 analysis, will be enrolled in the optional LTE phase if they consent and sign the ICF appendix for the optional LTE phase and meet the eligibility criteria for the optional LTE phase. When the Week 28 sponsor unblinding subsequently occurs, subjects that started the optional LTE phase but turn out not to be in Group 2A of the main study will be withdrawn from the optional LTE phase.

3. Subject must have received all 4 vaccinations of the main study.
4. Subject must be negative for HIV infection at the final main study visit at Week 72.
5. Subject must be willing/able to adhere to the prohibitions and restrictions for the optional LTE phase, as specified in the protocol and study procedures.

Any potential subject who meets any of the following exclusion criteria at the end of the main study will be excluded from participating in the optional LTE phase of the study. For the optional 2-year extension of the LTE phase, there are no exclusion criteria.

1. Subject has any condition for which, in the opinion of the investigator, participation would not be in the best interest of the subject (eg, compromise the well-being) or that could prevent, limit, or confound the protocol-specified assessments.

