11.2. Analysis Populations

The safety population will consist of all subjects who received at least one dose of study vaccine, and for whom any post-dose data is available.

The immunogenicity population will consist of all subjects who received at least one dose of study vaccine, and who have data from at least one evaluable post-dose blood sample.

The per protocol immunogenicity population will consist of all randomized and vaccinated subjects for whom immunogenicity data are available, excluding subject samples with major protocol deviations expecting to impact the immunogenicity outcomes (for example missed vaccinations, natural infections, etc).

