#### **4.3. Concomitant Medications**

The analysis of concomitant medications will be using the WHO drug dictionary as provided in the clinical database.

Based on their start and stop date, concomitant therapies will be reported in each period during which they were applied.

If a concomitant therapy record misses components of its start and/or stop dates (Day and/or month and/or year):

- In case of partial start or stop dates, the concomitant therapy records will be allocated to periods using the available partial information, without imputations. If, for example, only month and year are available, these will be compared to the month and the year of the periods, and the concomitant therapy record will be allocated to the period(s) where these date parts match.
- In case of a completely missing start date, the concomitant therapy will be considered as having started before the trial.

- In case of a completely missing end date, the concomitant therapy will be considered as ongoing at the end of the trial/cut-off date.

Concomitant therapies will be tabulated. There will be special attention to Acetaminophen, NSAIDS or Antihistamines to identify medication that can mask local or systemic solicited events in the 8 days after the vaccinations and to systemic glucocorticosteroids during the whole study duration for possible influence on the immunogenicity results. Systemic glucocorticosteroids will be flagged in the overall CM listing. Subjects taking PrEP during the study will be listed. After Week 72 only specific CM were to be collected (CTP Section 8) thus the reporting for the LTE will be limited to those as required by CTP.

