#### **4.5. Protocol Deviations**

All major protocol deviations will be listed.

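### SAP 2.3.2 narrows the protocol's open-ended per-protocol immunogenicity exclusion to a closed list, so some samples that the protocol would remove stay in the immunogenicity and long-term extension analyses

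*SAP*

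**What the plan says.** **Protocol 11.2** starts from all randomized and vaccinated subjects with immunogenicity data, "excluding subject samples with major protocol deviations expecting to impact the immunogenicity outcomes (for example missed vaccinations, natural infections, etc". The rule works on samples and is open-ended: the two named deviations are examples.

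**SAP 2.3.2** admits subjects who had at least the first three vaccinations on schedule (within 2 weeks), "have at least one measured post-dose blood sample collected and were not diagnosed with HIV during the study". Its one sample-level rule concerns dose 4. "Samples taken after Week 48 from subjects in the PPI population who missed the 4th vaccination", or had it out of window, are left out. There is no general deviation clause.

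**SAP 2.3.3** defines the LTE set as members of that population in group 2A with the full regimen and at least one LTE visit. It adds no sample rule. Under SAP 6.3, LTE time points are analyzed by the same methods as the main study.

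Elsewhere in the SAP:

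- Section 4.5: "All major protocol deviations will be listed".
- Section 4.3 gives special attention to "systemic glucocorticosteroids during the whole study duration for possible influence on the immunogenicity results", but the only consequence is a flag in a listing.
- Section 6.4 removes only BAMA and ICS values flagged as unreliable.
- Section 2.1 leaves out measurements after a missed second dose, which is again a dosing rule.

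**The concern.** Several entry criteria and on-study prohibitions bear directly on the antibody and T-cell readout: no HIV vaccine candidate, no recent blood or immunoglobulin products at entry, and no chronic or recurrent immunosuppression in the main study. Protocol 11.2 carries that protection into the analysis through its general clause. The SAP leaves the clause out and does not say why.

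Two things are at stake. First, a sample taken after, say, another Env-containing vaccine would be summarized as response to the study regimen, in a set labeled per-protocol. In the LTE it would count as durability, and the LTE has only one group, so no comparator would show the shift. Second, SAP section 1 says the analyses are done on fully unblinded data. If such a case turns up and no rule exists, either the sample stays or someone decides on its exclusion with the results in view.

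**Working it through.** **1. The plan's own figure.** Protocol 11.3 gives about 100 and 50 evaluable subjects, SD 0.4 on the log10 scale, a 1.5-fold difference, 1-sided 5% and 80% power.

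- Effect: log10(1.5) = 0.1761.
- SE = 0.4 × √(1/50 + 1/100) = 0.0693.
- Power = Φ(0.1761/0.0693 − 1.645) = Φ(0.897) = 81.5%.

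This agrees with the stated 80%. It is not in dispute and serves below only to price the remedy.

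**2. The two definitions side by side.** In the third column, "fits" assumes that the deviation is classed as major.

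| Event | Status in the protocol | Protocol 11.2 | SAP 2.3.2 and 2.3.3 |
|---|---|---|---|
| Missed dose | named example | excluded | covered (also mistimed doses) |
| HIV infection | named as natural infection | samples excluded | whole subject excluded |
| Another HIV vaccine candidate, main study or LTE | disallowed (4.3) | fits | kept |
| HIV vaccine candidate before entry | exclusion criterion 11 | fits | kept |
| Blood or immunoglobulin in the 3 months before entry | exclusion criterion 13 | fits | kept |
| Chronic or recurrent immunosuppression, main study | prohibited (4.3); stops vaccination (10.2) | fits | partly kept |
| Same, LTE, when medically required | permitted (4.3, 8) | not a deviation | kept |
| Blood or immunoglobulin during the study | no prohibition stated | not clearly a deviation | kept |

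Rows 3 to 6 are the gap; "kept" there presumes on-schedule dosing. In row 6 the gap is limited. If vaccination stops before dose 3, the subject leaves the set. If it stops between doses 3 and 4, samples after Week 48 go. What remains is samples from dose 3 to Week 48, which include the Week 28 primary time point, and samples after dose 4.

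**3. Size if affected samples are kept.** The documents give neither the LTE sample size nor the number affected nor the titer effect, so all three are assumptions. If k of n subjects are shifted m-fold, the geometric mean is multiplied by m^(k/n). With m = 10:

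| | k = 1 | k = 3 |
|---|---|---|
| n = 80 | 10^(1/80) = 1.029 | 10^(3/80) = 1.090 |
| n = 40 | 10^(1/40) = 1.059 | 10^(3/40) = 1.189 |

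For a share f of one arm and shifts of one-third, 3-fold and 10-fold, the multiplier is 0.98, 1.02 and 1.05 at f = 2%, and 0.95, 1.06 and 1.12 at f = 5%. One subject whose responder status changes moves the responder rate by 1/80 = 1.25 points or 1/40 = 2.5 points.

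**4. Cost of restoring the rule.** If 2%, 5% or 10% of evaluable subjects in each arm were removed, the power in step 1 would fall from 81.5% to 80.8%, 79.7% or 77.8%. The detectable difference would go from 1.49-fold to 1.49, 1.50 or 1.52.

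**The case against.** The strongest reply is that protocol section 11 leaves specifics to the SAP, and the SAP implements both of the protocol's named examples. HIV infection is even handled more strictly. LTE durability is an exploratory endpoint, no hypothesis is tested, and the listings let a reader see deviations. The shifts are also small against sampling error. With SD 0.4, the 95% interval for a geometric mean is a factor of 10^(1.96 × 0.4/√n), that is 1.22 at n=80 and 1.33 at n=40, and every shift in the first table of step 3 lies inside it. Safeguards exist as well: HIV vaccine candidates are barred at entry, at LTE entry and throughout the LTE, and subjects are asked at every LTE visit about other studies.

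Most of this stands as a limit on size. It does not close the gap, because removing a whole category of exclusion changes the population, and a listing does not change an estimate.

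A reader might also infer more than the documents support:

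- *That the exclusion was dropped altogether.* It was narrowed; dosing and HIV diagnosis remain.
- *That immunoglobulin given during the study should remove samples.* It is only an entry criterion, and in the LTE it would be recorded only if given in conjunction with an SAE (protocol 8).
- *That LTE samples under immunosuppression breach the protocol.* Protocol 4.3 says "During the optional LTE phase, use of these medications is discouraged, except when required by" the subject's medical condition, so medically required use is permitted and restoring 11.2 would not remove those samples.
- *That the further extension lifts the ban on other HIV vaccines.* Protocol 4.4 does say "For the optional 2-year extension of the LTE phase, there are no exclusion criteria", but the prohibition in 4.3 covers the whole LTE.

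**Conclusion.** The point holds as a mismatch between the two definitions. The SAP's per-protocol set omits the protocol's general sample-level exclusion, the LTE set inherits the omission, and no other SAP section restores it. It bites only for the deviations in rows 3 to 6 of the comparison, and only where the dosing conditions were met.

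The size of the effect is unknown and is nil if no such deviation occurred. The figures of about 3% (n=80) and 6% (n=40) for one subject rest on an assumed 10-fold shift and assumed sample sizes; immunosuppression would be expected to act in the opposite direction. Nothing in the documents shows that any reported result is wrong. The case for acting is that the rule is inexpensive to restore and cannot be written neutrally once the results are known.

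**What to change.** 1. In SAP 2.3.2, and expressly in 2.3.3, restore the sample-level exclusion of protocol 11.2 from the date of the deviation, and name the deviations: receipt of another HIV vaccine candidate in the main study or LTE; receipt of an HIV vaccine candidate before entry, or of blood or immunoglobulin products within 3 months before entry; and, for main-study samples, prohibited chronic or recurrent immunosuppression while it lasts. Samples from before the deviation stay. For the entry deviations, every study sample follows the event, so the subject drops out of the set.
2. Fix the list of affected samples without reference to the immunogenicity results, and document when and by whom (by role) it was fixed.
3. For immunosuppressant or systemic corticosteroid use that the protocol permits in the LTE, keep the samples in the main durability summary and add one sensitivity summary without them.
4. Add no exclusion for immunoglobulin given during the study.
5. SAP section 1 states that the Week 72 analysis is done and will not be rerun. Apply the rule directly to the LTE analysis and report it as a supplementary analysis for the main study.

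The cost is a short SAP amendment, one programmed sample flag and one extra set of LTE summaries. The inputs are already collected: major deviations, the LTE question about other studies, and the LTE record of immunosuppressants and corticosteroids. The loss of power is under 4 points even if 10% of subjects were removed.

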### 2.3.3. LTE Analysis Set

The Long Term Extension (LTE) population consists of all subjects in the Per-Protocol Immunogenicity Analysis Set, randomized in group 2A receiving the full vaccination regimen ‘Ad26.Mos4.HIV/Ad26.Mos4.HIV + gp140’ who had at least one visit in the long term extension part of the study.

### 2.4. Definition of Subgroups

The following subgroups will be investigated for the most relevant immunogenicity assays (more details in section 6.3):

- Country (Rwanda, USA)
- Ad26 VNA at baseline (<LLOQ, >=LLOQ)a
- Sex (Female, Male)
- Race (Caucasian, Black or African American, Asian, Otherb)
- BMI [<18.5; 18.5-<25; 25-<30; ≥30]a

## 3. INTERIM ANALYSIS AND DATA REVIEW COMMITTEE

A Data Review Committee (DRC) was planned to specifically review the safety data at three specific time points to ensure safety of the subjects:

- Review blinded safety data (2 weeks of follow up) after 15% of subjects had received their first injection to decide whether further dosing can continue;
- Review blinded safety data (2 weeks of follow up) after 30% of subjects had received their first injection to decide whether further dosing can continue;
- Review blinded safety data (2 weeks of follow up) after 30% of subjects had received their third injection to decide whether further dosing can continue.

These analyses are described in a separate DRC Charter.

## 4. SUBJECT INFORMATION

Subject information will be analyzed based on the FA analysis set unless otherwise specified.

Continuous variables will be summarized using the following statistics, as appropriate: number of observations, arithmetic mean (mean), 95% confidence interval (CI) for the mean, standard deviation (SD), standard error (SE), median, quartiles (Q1 and Q3), minimum and maximum. The minimum and maximum will be presented to the same number of decimal places as the original data. The mean and median will be rounded to one more decimal place than the original data, while the SD, SE and 95% CI to two more decimal places.

---

a Baseline Ad26 VNA and BMI will also be investigated as continuous variables.

b Subgroup “Other” should contain all remaining categories: Other, Multiple, American Indian or Alaska Native, etc.

#### **4.1. Demographics and Baseline Characteristics**

The following demographic and baseline characteristics will be summarized.

- Sex (Female/Male)
- Age (years)
- Race
- Ethnicity
- Region
- Country
- Height (cm)
- Weight (kg)
- BMI ( $\text{kg}/\text{m}^2$ ), calculated from the recording of baseline height and weight.

#### **4.2. Disposition Information**

Number and percentage of subjects that were 1) screened, 2) screening failures, 3) subjects meeting eligibility criteria but not randomized, 4) randomized and vaccinated, 5) randomized not vaccinated and 6) vaccinated but not randomized will be tabulated.

Number and percentage of subjects that completed and those who discontinued together with the reason(s) for discontinuation will be tabulated. This will be done for completion/vaccine discontinuation from further vaccination and from the trial at Week 72 and at the end of LTE. Number and percentage of subjects at each planned LTE visit will also be tabulated.

#### **4.3. Concomitant Medications**

The analysis of concomitant medications will be using the WHO drug dictionary as provided in the clinical database.

Based on their start and stop date, concomitant therapies will be reported in each period during which they were applied.

If a concomitant therapy record misses components of its start and/or stop dates (Day and/or month and/or year):

- In case of partial start or stop dates, the concomitant therapy records will be allocated to periods using the available partial information, without imputations. If, for example, only month and year are available, these will be compared to the month and the year of the periods, and the concomitant therapy record will be allocated to the period(s) where these date parts match.
- In case of a completely missing start date, the concomitant therapy will be considered as having started before the trial.

- In case of a completely missing end date, the concomitant therapy will be considered as ongoing at the end of the trial/cut-off date.

Concomitant therapies will be tabulated. There will be special attention to Acetaminophen, NSAIDS or Antihistamines to identify medication that can mask local or systemic solicited events in the 8 days after the vaccinations and to systemic glucocorticosteroids during the whole study duration for possible influence on the immunogenicity results. Systemic glucocorticosteroids will be flagged in the overall CM listing. Subjects taking PrEP during the study will be listed. After Week 72 only specific CM were to be collected (CTP Section 8) thus the reporting for the LTE will be limited to those as required by CTP.

#### **4.4. Exposure**

Number and percentage of subjects by number of received vaccinations will be tabulated.

Tabulation of vaccine administered within and outside the protocol-specified time windows (-1/+3 weeks of the planned vaccination and additional 2 weeks) will be provided as well.

#### **4.5. Protocol Deviations**

All major protocol deviations will be listed.

#### **4.6. Medical History**

Medical history data will be listed.

### **5. SAFETY**

The safety and tolerability endpoints are:

- Unsolicited AEs 28 days following each vaccination
- Solicited local and systemic AEs (reactogenicity), collected daily from day of vaccination for 7 days post-vaccination (day of vaccination and the subsequent 7 days).

The safety and tolerability analysis will be performed on the FA set. Specifically, the analysis for solicited adverse events will be done on those subjects in the FA set for whom reactogenicity assessments are available in the database (either via on-site assessments or via the diary pages of the CRF).

Safety data will be tabulated per period by regimen. Only the active periods will be shown in the tables (AE, Lab, VS), except for SAEs. In addition, for a selection of tables (AE, Lab), tabulations per subject by vaccine and per dose by vaccine will be provided.

In the ‘per subject by vaccine’ analysis, the safety will be presented per periods (post-dose 1, 2, 3, 4) by vaccine rather than by regimen. A ‘post any dose’ period (= regimen phase in section 2.1) will be added, that summarizes the safety after all administered doses of a vaccine. The post-any-dose period allows determining how many subjects reported events after administration of a certain vaccine regardless the number of doses. Each subject is counted only once. In case a subject has the same event after more than one dose, it is counted only once (and in case of showing attributes,

the worst corresponding attribute is shown) in the post-any dose period. The denominator is the number of subjects that received the considered vaccine in the considered period.

In the ‘per dose by vaccine’ analysis, the safety will also be presented by vaccine. This table allows determining the incidence of events per administered dose of a certain vaccine. For example, if a subject has the same event at least once after dose 1 and at least once after dose 2 of the same vaccine, it is counted 2 times (so the numerator is the sum of post-dose 1, 2, 3 and 4 events in the “per subject by vaccine” table). In case of showing attributes, the worst corresponding attribute of each period are shown. The denominator is the total number of doses administered of the considered vaccine over all subjects.

At the 3th and 4th vaccination timepoint two vaccines should be administered at two different injection sites (left/right deltoid). The local solicited events should be linked to the medication injected in that specific injection site. However for some subjects the link between local AE and injection site might be unavailable, so the AE will be attributed to both medications received by the subject (e.g. if a subject receiving Ad26 + gp140 HD with AE “Erythema”: Erythema will be counted for Ad26 and for gp140 HD). Systemic solicited and unsolicited AE will be reported under both the administered medications.

